Overall Study Design: The Enhanced, EHR-facilitated Cancer Symptom Control (E2C2) is a pragmatic, cluster-randomized clinical trial that will rigorously assess the impact of the intervention in controlling SPPADE symptoms among patients with cancer spanning the cure-directed, survivorship, and palliative phases of disease management, while also exploring factors relevant to its implementation. The E2C2 trial is population based; all patients receiving care for solid tumors at the MC Cancer Center Rochester (MCR) will be included in the study sample irrespective of cancer type or stage. A similar sample will be included from community clinics within the Mayo Clinic Health System in Minnesota and Wisconsin, with the addition of malignant hematology patients at those community sites. Patients will be assigned the ePRO "Basic Symptom and Function Screen" (BSFS) questionnaire via their EHR approximately 4 days prior to their oncology appointment (in-clinic or virtual visit) as the standard of care process. The EHR algorithm will be set to assign questionnaires no more than every 2 weeks. The patient will have the ability to complete the BSFS via their portal but will be prompted to complete it via welcome tablet at check in if they do not. Additionally, if patients do not respond to questionnaires via portal or welcome tablet, they will be given an opportunity to complete it via Interactive Voice Response, otherwise known as IVR. When a patient fails to complete their assigned BSFS questionnaire, they will receive an automated phone call and will be prompted to answer the questions via touchpad. While Mayo Clinic is using an external vendor (IPT), all data is maintained on Mayo Clinic servers. We are not releasing data to IPT at any point in time. The ePRO (questionnaire) Health platform resides on our server and is not going outside of the firewall. Data going to the platform is transient in nature and is purged once the results are sent back into Epic. SPAD approval has been granted and there are Business Associate Agreements (BAA) and Information Security Agreements (ISA) in place, which covers how PHI can be used and stored. The trial's stepped wedge design (SWD) will randomize the order of E2C2 implementation among 15 clusters. Clusters will be defined at the level of the cancer care team and will be randomized to one of five different tranches to receive the implementation at staggered 8 month intervals. Between 2 to 20 oncologists/hematologists and mid-level providers will comprise each of the 15 clusters. Clusters will be randomized to initiate the E2C2 intervention at each of the steps. This design will allow data to be sequentially collected from all clusters for a minimum of 7 months during pre-E2C2 usual care. This stepped wedge design will allow us to compare outcomes for each cluster both across intervention groups and with historical controls at the same clinic, providing a rigorous assessment of the impact of E2C2 on controlling SPPADE symptoms among patients with cancer while also exploring factors relevant to its implementation across all sites.

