Quantitative data collection and analysis. In order to understand variation in the use of the E2C2 symptom management strategies, we will first use data from the EHR to identify if the intervention is similarly accessed/adopted and if symptom management and utilization patterns are similar across age groups and by patients in rural and urban areas. We will calculate ePRO response rates (dividing the number of ePROs returned/the number sent) during the pre-E2C2 usual care period and then again during the intervention period, comparing rates by age, urban/rural residence, and age/rural residence. To analyze response rate data, we will use both simple unadjusted descriptive statistics as well as generalized regression models. We will calculate simple proportions of response rates for the total population and by age and urban/rural status. We will then create regression models to determine predictors of being a high responder. Additional explanatory variables will include patient demographics (e.g., employment status, insurance status, gender), cancer type and stage and cluster. Response rates at each time point will be calculated for analyses, and models will include a random intercept to account for repeated measures over patients. We will then aggregate data and examine trends over time to determine if, over time, response rates have increased significantly. Similarly, we will calculate responses to PROMIS CAT scores (individually and composite scores) during the pre-E2C2 usual care period and then again during the intervention period, comparing rates by age, urban/rural residence, and age/rural residence. For the PROMIS CAT scores, we will use a similar analytic approach as with the response rate analysis.

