Automated Symptom Monitoring: Following the transition from pre-E2C2 usual care to the E2C2 intervention, the ePROs used to assess SPPADE symptoms, physical function impairment, social participation, distress, and QoL will not change, however, assessment frequency will increase, particularly for symptomatic patients. After initiating E2C2, the Symptom Control Bundle will be activated and patients and clinicians will be able to access graphic displays for SPPADE score tracking, and patients will be able to enter ePROM data via a telephonic symptom assessment in addition to the web, smart phone, and tablet modes.

Presentation of symptom data to patients and clinicians. For PROM data to be useful in clinical practice, patients and clinicians need to understand what the scores mean. In order to facilitate intuitive ePROM interpretation, the E2C2 intervention will include a dedicated view in the clinician-facing Synopsis section of the Epic EHR and in the patient-facing My Chart interface. The views will be identical for both patients and clinicians to support communication and will be specified per the findings of Snyder et al. to optimize accurate interpretation.⁸⁰ Data collected regarding symptom intensity and context will also be presented to clinicians in brief auto-generated text that will populate their clinical notes with a patient's longitudinal SPPADE scores and a hyperlink to the graphic Synopsis view. Presenting data to clinicians in graphic form for decision support has been shown to have a small to moderate effect size in improving patient outcomes.^{81,82}

EHR Triage and Decision Support Algorithms. EHR algorithms are foundational to the E2C2 intervention. Algorithms populated by automatically abstracted PROM and clinical data from the EHR will determine which symptom-directed services are offered to patients at multiple points in the intervention. Algorithms will be built into Epic using specification capabilities integral to the foundation system and available in all Epic iterations after 2014.

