Specific Aim 2 Analyses. We will summarize patient characteristics (sex, age, insurance status) by intervention status (baseline, intervention). We will also summarize all survey responses by cluster implementation status, including clinician characteristics (age, sex, years of practice). All patients will be analyzed on an intention to treat status; this principle will be extended to the cluster status, so that delays in implementation of an intervention will not affect the intervention status of patients.¹⁰¹ All methods will account for correlation of outcomes within clusters and across patients. As a secondary objective of this aim, we will assess the change in clinician survey constructs over time. This analysis will include each clinician with at least two completed surveys at least 6 months apart.

As in Aim 1, we will also assess the effect of process measures on SPPADE scores and other clinical outcomes. We will use models appropriate for count data, selecting standard or zero-inflated Poisson or negative binomial models according to Aikake's Information Criteria, or logit models for binary measures. For each outcome we will estimate a) bivariate models including only one survey score; b) a model with all scores; and c) a final model which also includes clinician characteristics.

Aim 3

Endpoints

Primary:

SPPADE and physical function NRSs will serve as both the E2C2 primary outcome and a critical component of the E2C2 intervention since NRS scores populate the EHR algorithms that determine whether patients are triaged to Level 1 or 2,

and whether patients are offered specific intervention components (education, medications, etc.). Patients will complete NRSs for SPPADE symptoms and physical function prior to medical oncology clinic appointments at all stages of the trial, i.e., prior to and after E2C2 initiation. ePROs will be more frequently administered to symptomatic patients outside of their appointment-linked assessments as part of the intervention. *To avoid potential bias from oversampling of symptomatic patients, only SPPADE symptom NRSs collected in association with clinic appointments will be included in the primary analysis.*

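### The ePRO response rate is compared before and after go-live as returned over sent, yet go-live adds off-visit questionnaires to what is sent, so the rate can shift either way with no change in patients' responding

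*Combined protocol and SAP*

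**What the plan says.** The section on quantitative data collection and analysis, under patient enrollment, data collection and analysis, obtains the response rate by "dividing the number of ePROs returned/the number sent". It compares the rate "during the pre-E2C2 usual care period and then again during the intervention period", by age, by urban or rural residence, and by the two combined. It plans simple proportions, regression models with a patient random intercept, a model for predictors of being a high responder, and an aggregate look at trends to "determine if, over time, response rates have increased significantly". On covariates it says: "Additional explanatory variables will include patient demographics", followed by cancer type and stage and cluster. It names no term for the kind of send or for symptom status.

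Three other sections determine what counts as sent:

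- Overall Study Design: the standard-of-care BSFS is assigned "approximately 4 days prior to their oncology appointment". Patients can use the portal and "will be prompted to complete it via welcome tablet at check in if they do not". An automated telephone call (IVR) follows if the questionnaire is still not completed. Assignment is capped at once every two weeks.
- Automated Symptom Monitoring, under Interventions: after the switch to E2C2, "assessment frequency will increase, particularly for symptomatic patients". Telephone entry is listed among the things that become available at that point.
- Endpoints, Primary: "ePROs will be more frequently administered to symptomatic patients outside of their appointment-linked assessments as part of the intervention". To avoid oversampling symptomatic patients, that section restricts the primary analysis to NRS scores tied to clinic appointments.

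The restriction is stated for the primary analysis only. The text on reporting mode and rates, under the secondary endpoints, does not extend it to response rates.

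**The concern.** The sends described for usual care are tied to a visit, with a tablet prompt at check-in. After go-live the denominator also holds sends that have no visit, and therefore no check-in, and that go to patients selected for their symptoms. The ratio keeps its name but covers a different mix of questionnaires. The plan recognises this mix for the primary scores and removes it there. It leaves it in the response rate.

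This is separate from any calendar trend, although it can look like one. Clusters cross over three at a time at five steps, so the off-visit share of all sends would build up across the trial. A change in composition could then be read as a trend in responding.

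The response rate is a main quantitative measure for Aim 3. The plan gives special emphasis to disparities among elderly and rural patients, and the patient interviews are to be balanced on responders and non-responders. At stake are whether an increase is declared, who is labelled a high responder (a term that the section does not define further), and possibly the age and rural contrasts.

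**Working it through.** **Stated figure.** The documents give no response rate, off-visit send count, sample size or power for this analysis, so there is nothing to reproduce. All rates and shares below are assumptions.

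**Formula.** Let r_visit be the response to appointment-linked sends, taken as identical in both phases; r_off the response to off-visit sends; and s the off-visit share of sends after go-live.

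- Rate before go-live = r_visit
- Rate after go-live = (1 − s) × r_visit + s × r_off
- Shift with no change in behaviour = s × (r_off − r_visit)

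The shift depends on r_visit only through the difference. In percentage points:

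| r_off − r_visit | s = 10% | s = 20% | s = 30% | s = 50% |
|---|---|---|---|---|
| −30 | −3.0 | −6.0 | −9.0 | −15.0 |
| −15 | −1.5 | −3.0 | −4.5 | −7.5 |
| 0 | 0 | 0 | 0 | 0 |
| +15 | +1.5 | +3.0 | +4.5 | +7.5 |

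**Worked case.** Take 1,000 patients with 4 appointment-linked sends each and 60% returned. Suppose 30% are symptomatic and get 4 extra off-visit sends each.

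- Before: sent 4,000, returned 2,400, rate 60%.
- After: sent 4,000 + 300 × 4 = 5,200, so s = 1,200/5,200 = 23.1%.
- If 40% of off-visit sends are returned: (2,400 + 480)/5,200 = 2,880/5,200 = 55.4%.
- If 75% are returned: (2,400 + 900)/5,200 = 3,300/5,200 = 63.5%.

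Appointment-linked response is 60% throughout.

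**Subgroups.** Take two groups with appointment-linked response of 60%, one with s = 30% and the other with s = 10%.

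- Off-visit response 40% in both: 0.7 × 60 + 0.3 × 40 = 54.0 against 0.9 × 60 + 0.1 × 40 = 58.0, a gap of −4.0 points.
- Off-visit response 75% in both: 0.7 × 60 + 0.3 × 75 = 64.5 against 0.9 × 60 + 0.1 × 75 = 61.5, a gap of +3.0 points.
- Same s and same off-visit response in both groups: the gap is zero.

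**Whether the planned model removes it.** The patient random intercept can absorb part of the between-patient mix. It does nothing for the planned simple proportions. Nor does it account for a difference, within one patient, between sends with a check-in prompt and sends without one.

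**After restriction.** If both phases count appointment-linked sends only, s = 0 and the shift is zero by construction.

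**The case against.** A reader might infer that the rate must fall after go-live because off-visit sends lack the tablet. The documents do not support that. Symptomatic patients are identified largely from their BSFS answers (Triage to Level 1 or 2), so the extra questionnaires would go mainly to people who have already responded. The appointment-linked denominator also contains people who never respond. Off-visit response could therefore be the higher of the two. The automated call is described without being confined to visit-linked assignments, so off-visit sends may have a fallback too. This objection stands: the direction is unknown.

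The largest shifts also need a large off-visit share. An s of 50% means one off-visit send per appointment-linked send. If 30% of patients are symptomatic, that is 1/0.3 = 3.3 extra sends per visit for each of them. If the two-week cap covers off-visit sends, their visits would have to be at least (3.3 + 1) × 2, or about 8.7 weeks, apart. The plan itself expects a large part of the cohort to report few symptoms. The right-hand column of the table is therefore an outer bound.

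Off-visit ePROs are part of the intervention, and one stated purpose of the section is to see whether the intervention is taken up equally across groups. Within the intervention phase, response to those questionnaires is a fair measure of reach and should be kept. This also stands, and the fix retains it.

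None of this removes the gap. The pre/post and trend comparisons still use a denominator whose content changes at go-live.

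**Conclusion.** The point holds as a fault in how the response rate is defined. As written, the pre/post and trend comparisons mix a change in what is sent with a change in how patients respond. The shift is s × (r_off − r_visit), and it is zero only if off-visit and appointment-linked response are equal. With s assumed between 10% and 50%, it runs from −15 to 0 points when off-visit response is 0 to 30 points lower, and from +1.5 to +7.5 points when it is 15 points higher. An upward shift would look like the improvement that the plan is testing for.

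Two stronger readings should be avoided. One is that a false age or rural disparity will appear. That requires the off-visit share or the off-visit response to differ between the groups, and the documents do not say that either does. The other is that the trial's main result is affected. It is not, because the primary SPPADE analysis is already limited to appointment-linked scores.

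A related uncertainty remains. Overall Study Design describes the automated call as part of the general process, while Automated Symptom Monitoring lists telephone entry as new with E2C2. If it starts at go-live, appointment-linked response also gains a mode at that point, and the restriction alone would not make the two phases alike.

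**What to change.** 1. For the pre/post and trend comparisons, overall and by age and rural residence, and for the high-responder definition, set the rate in both phases to appointment-linked BSFS returned divided by appointment-linked BSFS assigned. This is the restriction that the primary endpoint section already uses.
2. Report response to off-visit ePROs separately, for the intervention phase only, also by age and rural residence, as a measure of reach.
3. Reconcile Overall Study Design with Automated Symptom Monitoring on whether telephone or IVR entry is available before go-live. If it starts at go-live, report appointment-linked response by mode as well.

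The cost is a few sentences in the analysis plan and one filter on the type of send. The primary analysis already needs returned scores to be identifiable as appointment-linked. The denominator needs the same flag on assignments that were not returned. The documents do not say that this is stored, so it should be confirmed with the EHR team. No new patient data are needed, and with item 2 the off-visit information is kept.

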E2C2 / 18-007779

Enhanced, EHR-facilitated Cancer Symptom Control (E2C2)
Pragmatic Clinical Trial

NCT03892967

Document Date: 03/04/2025

IRB Minimal Risk Protocol Template

General Study Information

Principal Investigator: [name], MSCE

Study Title: Enhanced, EHR-facilitated Cancer Symptom Control (E2C2) trial

Protocol version number: March 4, 2025 Version 24

Research Question and Aims

Hypothesis: Collaborative care management for control of moderate or worse sleep disturbance, pain, physical function impairment, anxiety, depression, fatigue (SPPADE symptoms), and physical dysfunction among cancer survivors and patients with cancer will improve quality of life, symptom severity, and adherence to cancer treatment, and will also reduce need for acute care.

Aims:

Specific Aim 1. Conduct a cluster randomized pragmatic trial with a stepped wedge design to test the hypothesis that a symptom control-focused E2C2 intervention will significantly reduce SPPADE symptom and physical dysfunction scores; reduce unplanned hospitalizations, emergency department (ED) visits, and intensive care unit (ICU) admissions; improve adherence to cancer therapies; and improve self-reported quality of life.

H1a. SPPADE symptom scores will improve more, relative to prior scores, for patients who have been exposed to the intervention when compared with the improvement of patients that are not exposed.

H1b. Among patients who report moderate or worse symptoms, SPPADE symptom scores will improve more for patients who have been exposed to the intervention when compared with the improvement of patients that are not exposed.

Specific Aim 2. Evaluate the hypothesis that use of a multifaceted, evidence-based implementation strategy to support adoption and use of the E2C2 system will result in improvements in implementation and clinical outcomes.

Specific Aim 3. Conduct a mixed methods evaluation to detect, understand and reduce disparities in the adoption and implementation of the E2C2 intervention among elderly and rural-dwelling patients with cancer.

Background:

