
The primary outcomes of the trial are a bundle of 6 SPPADE symptom and function scores assessed with numerical rating scales (NRSs) collected in association with medical oncology clinic appointments. The primary analysis will test differences in the change in mean joint SPPADE symptom NRS scores in all participants, and in those who experience elevated (4-10/10) symptoms, between participants who are exposed to the intervention and those who are not. Secondary outcomes will include PROMIS-CAT measures for anxiety, depression, pain, and physical function, assessed up to every four months depending on visit frequency. Additional secondary outcomes will include health care utilization, adherence to cancer treatment, and survival. Variation in ePRO response rates and outcomes will be assessed for all participants, but special emphasis will also be given to disparities in outcomes among elderly and rurally based patients.

Process measures will capture stakeholders' use of the EHR graphic and decision support tools and will be abstracted from the EHR. All analyses will be performed using methods appropriate for cluster randomized stepped wedge trials. In parallel with conduct of the E2C2 trial, mixed methods will be used to comprehensively assess system usability, multi-stakeholder experience, and barriers and facilitators for stakeholders' use of the system. Qualitative interviews will also

be conducted to understand possible reasons for disparities in the adoption and implementation of the E2C2 intervention among elderly and rural-dwelling patients with cancer.

Cancer Patient Enrollment: This is a population-based study, where all eligible patients seen by clinicians at the Medical Oncology Clinic in Rochester and hematology/oncology in the Midwest Mayo Clinic Health Systems (MCHS) will be enrolled. This inclusive enrollment approach substantially increases the generalizability and external validity of our real-world pragmatic trial. Rochester campus will act as primary research site and there will be no study team responsibilities at any of the MCHS sites.

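### For ePRO response rates and PROMIS CAT scores, Aim 3 specifies no estimate of the change in the age or rural gap and no adjustment for study step, so calendar drift could pass for an E2C2 effect

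*Combined protocol and SAP*

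**What the plan says.** Specific Aim 3 is a mixed methods evaluation meant to "detect, understand and reduce disparities in the adoption and implementation of the E2C2 intervention among elderly and rural-dwelling patients with cancer". The Study Design and Methods section adds that "special emphasis will also be given to disparities in outcomes among elderly and rurally based patients".

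The analysis is described under Patient enrollment, data collection and analysis, in the paragraph on quantitative data. Response rates (questionnaires returned over questionnaires sent) are calculated "during the pre-E2C2 usual care period and then again during the intervention period", "comparing rates by age, urban/rural residence, and age/rural residence". The modelling step is: "We will then create regression models to determine predictors of being a high responder". On covariates: "Additional explanatory variables will include patient demographics (e.g., employment status, insurance status, gender), cancer type and stage and cluster". On correlation: "models will include a random intercept to account for repeated measures over patients". The only analysis over time is an aggregate trend in response rates, not split by age or residence. PROMIS CAT scores are to be handled in a similar way.

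That paragraph names no intervention indicator, no study-step term and no interaction of age or residence with the intervention. Models (1) and (2) in the Data Analysis Plan carry patient factors as main effects only, and rural residence is not among the covariates listed under Specific Aim 1 Analyses.

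**The concern.** Whether a disparity shrinks or grows under E2C2 is a question about a change in a gap. It needs a contrast between periods, with its uncertainty. The plan gives the ingredients (a gap before, a gap after) but not the contrast.

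In a stepped wedge the intervention data come later than the control data by design. A gap may move over some years for reasons that have nothing to do with E2C2, such as changing portal use or changing referral patterns. A pooled before/after comparison without step terms assigns all of that movement to E2C2. The trial could then credit or blame E2C2 for a change in an age or rural disparity that it did not cause.

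The plan deals with both issues elsewhere. H1a adjusts for study period, and H1b interacts elevated symptoms with the intervention. Neither device is carried over to Aim 3.

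**Working it through.** The plan gives no sample size, power or effect size for Aim 3, so there is no figure of its own to reproduce. Its only power statement concerns the Aim 1 symptom scores and has no bearing here.

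**Inputs.** From Figure 1 and the Allocation paragraph: 15 clusters, 6 steps, 5 sequences of 3 clusters, later steps 8 months long. The first period is 7 months in the text and 6 months in the key to Figure 1. Drift sizes, response rates and patient numbers below are assumptions.

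**1. Distance in steps.**
- Control cluster-periods at steps 1 to 6: 15, 12, 9, 6, 3, 0 (total 45). Mean step = (15×1 + 12×2 + 9×3 + 6×4 + 3×5)/45 = 105/45 = 2.33.
- Intervention cluster-periods: 0, 3, 6, 9, 12, 15 (total 45). Mean step = (3×2 + 6×3 + 9×4 + 12×5 + 15×6)/45 = 210/45 = 4.67.
- Difference: 2.33 steps. Each cluster-period counts equally here; unequal patient numbers would shift the figure somewhat.

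**2. Distance in months.** Weighting period midpoints by length gives 31.3 − 13.9 = 17.4 months with a 6-month first period, and 32.3 − 14.3 = 18.1 months (before rounding) with 7 months. At 8 months for every step it is 2.33 × 8 = 18.7. So it is about 17 to 19 months, and the disagreement over the first period hardly matters.

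**3. Spurious change in the gap.** Suppose the gap drifts linearly by d points per step and E2C2 has no effect on it. The pooled before/after difference in the gap is d × 2.33.

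| Assumed drift per step | Apparent change in gap |
|---|---|
| 0.5 | 1.17 |
| 1 | 2.33 |
| 2 | 4.67 |

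**4. The same drift with adjustment.** Write the gap in cluster m at step w as a(m) + c(w) + θX(m,w), where X marks intervention cluster-periods. A drift that depends only on w is absorbed by c(w), so the estimate of θ is 0. Least squares on the 90 cells with a drift of 1 point per step returns 0.00. On patient-level data, c(w) is the group-by-step term, a(m) the group-by-cluster term and θ the group-by-intervention term.

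**5. Mix of sites.** Community clusters supply 13 of the 45 control and 11 of the 45 intervention cluster-periods (Rochester 32 and 34). The shift is small. The listed cluster covariate covers differences in level but not gaps that differ between clusters.

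**6. Precision.** Assume response of 60% versus 55%, independent patients and n per group per period. The standard error of the change in the gap is √[2(0.60×0.40 + 0.55×0.45)/n] = √(0.975/n). The last column is power to detect a halving of the gap (2.5 points).

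| n | Standard error (points) | 95% half-width (points) | Power |
|---|---|---|---|
| 250 | 6.2 | 12.2 | 6% |
| 500 | 4.4 | 8.7 | 8% |
| 1000 | 3.1 | 6.1 | 12% |

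Clustering would widen these intervals. Larger numbers, which a population-based trial may well have, would narrow them.

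**The case against.** The strongest reply is that the plan is under-specified rather than wrong. It does not say that separate models will be fitted in each period. Rates at each time point and a patient random intercept fit a single longitudinal model at least as well. That stands. A reader might infer that two period-specific significance tests will be set against each other, so that a gap significant in one period only is reported as a change. The documents do not say so. If it were done with two independent tests of the same true gap, each with power p, they would disagree with probability 2p(1−p): 50% at p = 0.5 and 32% at p = 0.8. Those figures need an unplanned step, an assumed power and independence, although the same clusters contribute to both periods. Nothing here rests on them.

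A second reply is that Aim 3 concerns adoption and implementation, and that its numbers feed the patient interviews. Uptake of E2C2 components exists only after go-live, so comparing it within that period is correct. That also stands, and it limits the point to response rates and PROMIS CAT scores, which the plan compares in both periods.

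A third reply cites the general promise to use methods suited to stepped wedge trials. It names no contrast, so it does not settle what will be estimated.

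A reader might also infer from the bare Aim 3 heading in the Data Analysis Plan that no Aim 3 analysis exists. The documents do not support that: the analysis is described under patient data collection, and text may have been lost in extraction.

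**Conclusion.** The point holds as an omission for two outcomes, ePRO response rates and PROMIS CAT scores. The plan describes age and rural comparisons in both periods but specifies neither the change in the gap attributable to E2C2 nor an adjustment for study step.

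The separation of 2.33 steps follows from Figure 1 with equal weight per cluster-period. The resulting error scales with the drift, whose size and direction the documents do not give. The range of 1.17 to 4.67 points shows what linear drifts of 0.5 to 2 points per step would do; it is not a prediction. The error arises if the pooled before and after gaps are read as the effect of E2C2, which nothing in the plan prevents.

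**What to change.** For response rates and PROMIS CAT scores, fit one model over both periods with intervention, study step, cluster, age group and rural status, plus group-by-step and group-by-intervention terms, and group-by-cluster terms if they can be estimated. Report the group-by-intervention contrast, the change in the gap, with its interval.

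For response, use one binary record per assigned questionnaire. Ideally restrict it to appointment-linked questionnaires: assessment frequency rises after go-live, especially for symptomatic patients, so the denominator may differ between periods. The plan makes that restriction only for the primary analysis.

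Keep comparisons of component uptake within the intervention period. For the NRS outcomes, fit the same interaction only in separate secondary survey-level models, one score at a time, with rural status added. It should stay out of the primary joint model, which the plan already allows may not be estimable.

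The cost is SAP wording and a few model terms. Age and the 9-digit zip code are already captured. The drawback is imprecision, so the results should be read as intervals and not as verdicts on significance.

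### The Aim 3 high-responder regression mixes willingness to respond with the number of questionnaires sent

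*Combined protocol and SAP*

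**What the plan says.** Under Patient enrollment, data collection and analysis, the paragraph on quantitative data collection defines the response measure: "We will calculate ePRO response rates (dividing the number of ePROs returned/the number sent) during the pre-E2C2 usual care period", and again in the intervention period, "comparing rates by age, urban/rural residence, and age/rural residence". After simple proportions, it adds: "We will then create regression models to determine predictors of being a high responder". It gives no cut, time window or minimum number sent. On covariates it says: "Additional explanatory variables will include patient demographics (e.g., employment status, insurance status, gender), cancer type and stage and cluster". It also says that "models will include a random intercept to account for repeated measures over patients".

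The number sent is not fixed by design. Overall Study Design assigns the symptom "questionnaire via their EHR approximately 4 days prior to their oncology appointment", with a limit: "The EHR algorithm will be set to assign questionnaires no more than every 2 weeks". The Automated Symptom Monitoring section says that assessment becomes more frequent once E2C2 starts, above all in symptomatic patients. The Endpoints section restricts the primary symptom analysis to appointment-linked scores. No such restriction is stated for the response analysis.

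**The concern.** A patient sent one questionnaire can only have a response rate of 0% or 100%. A patient sent ten will usually have a rate near his or her own underlying probability. When these rates are cut into high and not high, patients with the same willingness to respond have different chances of passing the cut, simply because their denominators differ.

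Aim 3 is meant to detect disparities among elderly and rural patients, and the quantitative results feed into the interviews. If a compared group, or the intervention period, has systematically more or fewer questionnaires per patient, the regression can attribute to willingness what is only a difference in count. It can also mask a real difference.

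**Working it through.** The documents give no response probability, cut, distribution of number sent or power for this analysis, so there is no figure to reproduce. All inputs below are assumptions, shown as ranges.

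**Formula.** A patient sent n questionnaires, each returned with probability p, passes cut c with probability P(X ≥ ⌈cn⌉), where X ~ Binomial(n, p). Each group's share is the average over its values of n, equally weighted. The spurious odds ratio (OR) is [a/(1−a)] / [b/(1−b)], where a and b are the shares in the groups sent fewer and more.

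**Worked case.** p = 0.6 for everyone, c = 80%.
- n = 1 to 4: 0.600, 0.360, 0.216, 0.130. Mean 0.326.
- n = 5 to 12: 0.337, 0.233, 0.159, 0.106, 0.071, 0.167, 0.119, 0.083. Mean 0.159.
- OR = (0.326/0.674) / (0.159/0.841) ≈ 2.6, with no difference in willingness.

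**Extreme case: 1–4 v 5–12 sent, no overlap.** The beta-binomial columns let p vary between patients (concentration 4, that is, a within-patient correlation of 1/(4+1) = 0.2).

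| mean p | cut | shares, common p | OR | shares, beta-binomial | OR |
|---|---|---|---|---|---|
| 0.5 | 50% | 61% v 57% | 1.20 | 58% v 54% | 1.21 |
| 0.5 | 75% | 30% v 9% | 4.06 | 34% v 23% | 1.76 |
| 0.5 | 80% | 23% v 7% | 4.40 | 29% v 19% | 1.72 |
| 0.6 | 50% | 73% v 78% | 0.77 | 69% v 68% | 1.05 |
| 0.6 | 75% | 41% v 22% | 2.44 | 45% v 36% | 1.49 |
| 0.6 | 80% | 33% v 16% | 2.55 | 39% v 31% | 1.43 |
| 0.7 | 50% | 83% v 92% | 0.45 | 79% v 81% | 0.91 |
| 0.7 | 75% | 55% v 44% | 1.56 | 58% v 51% | 1.28 |
| 0.7 | 80% | 44% v 34% | 1.58 | 50% v 46% | 1.20 |

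**Milder cases: overlapping numbers sent.** The ranges 1–8 v 1–12, 2–8 v 3–10, 3–8 v 4–10 and 4–10 v 5–12 over the same grid give ORs of 0.75 to 1.53 with a common p. With the beta-binomial they run from 0.94 to 1.17, and 28 of 36 cells lie within 10% of 1.

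**Is the unequal denominator the cause?** A null simulation used 4,000 runs, 500 patients per group, p = 0.6 in both groups and a nominal 5% level.
- 3 v 10 sent: comparing high-responder shares rejected in about 100%, 51% and 49% of runs at cuts of 50%, 75% and 80%. With between-patient correlation 0.3 it rejected in 52%, 27% and 26%.
- The same data compared as undichotomised patient rates: 4.3% to 5.5%.
- 6 v 6 sent, dichotomised: 4.7% to 5.5%.

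The excess thus needs both the dichotomy and unequal numbers sent.

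**The case against.** Four arguments weigh on the other side.

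- **Other analyses exist.** The same paragraph plans simple proportions by age and urban/rural status, and the Reporting mode and rates section plans mixed models for reporting frequency. Neither is dichotomised. This stands: a reader might infer that the whole Aim 3 response analysis is unsound, and the documents do not support that.
- **The class is inferred.** The text does not say that each patient gets one class from all follow-up. Rates at each time point and a patient random intercept point to a repeated outcome. This stands in part. If a time point covers several questionnaires, the dependence on number sent remains within it, and a random intercept does not remove it. If the unit is the single questionnaire the problem vanishes, but then high responder has no meaning and the text should say so.
- **The link with age and residence is assumed.** A reader might infer that elderly or rural patients have fewer visits. No section says so. Cancer type, stage and cluster, which are in the model, may also absorb part of visit frequency; the calculation gives no credit for that.
- **Not every cut misleads, and the direction need not flip.** At p = 0.5 all three cuts give an OR above 1. Some pairs coincide: 4 v 8 sent at p = 0.6 and a 50% cut gives 0.821 v 0.826. So a claim that the artefact appears at every cut and reverses with it would be too strong. What stands is that fixing a cut does not in general cure the problem.

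**Conclusion.** The concern holds for the high-responder regression and for nothing else in the response analysis. As written, the outcome generally depends on number sent as well as on willingness, and no listed covariate addresses this directly. A spurious or masked gap follows only if age, rural residence or study period is related to number sent. For study period the stated rise in assessment frequency makes this plausible if the extra assessments are counted; for age and residence it is purely an assumption.

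The size is uncertain. The OR of 0.45 to 4.4 belongs to non-overlapping groups with one common response probability and should be read as an outer bound within the assumed grid (response 50% to 70%, cuts 50% to 80%). Strong patient heterogeneity reduces it to 0.9 to 1.8. Heterogeneity with overlapping numbers sent leaves about 0.94 to 1.17. The direction depends on the cut and the response rate. Severity is low to moderate: H1a and H1b are untouched, but a better model is available on the same data.

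**What to change.** Replace the high-responder regression with a mixed logistic model whose unit is each assigned questionnaire (returned yes or no). Include a patient random intercept, cluster, study period, age group, rural residence, the age-by-rural interaction and the covariates already listed. Report model-based response probabilities by group. Add a sensitivity analysis with number sent or visit frequency as a covariate, since visit count may itself be related to responding. State whether questionnaires sent outside appointments are counted.

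If a high-responder class is kept, use it descriptively only, with cut, time window and minimum number sent fixed in advance.

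The cost is SAP wording and minor analysis work. The EHR data are the same, and the patient random intercept is already planned.
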